## 9.8. Quality Control

In order to ensure the quality and integrity of the study results, the electronic data capture system will contain automatic checks for data completeness and to identify inconsistent data and respective queries will be generated when necessary. Data and queries will be remotely monitored for consistency and completeness. The study monitor will only review on site the data for which patients have consented.

## 9.9. Limitations of the Research Methods

This study has the characteristic disadvantages of retrospective studies, for example selection bias, information bias and missing values.

In order to reduce selection bias, subject's eligibility criteria have been well defined. However, this is not a type of bias easy to prevent or measure. A selection bias introduced by the choice of sites that contribute patient data cannot totally be avoided. However, a selection of sites in multiple countries will help to reduce this kind of bias. Countries selected for this study include

those in which an EAP for idelalisib in refractory FL patients has been running since the time of MA for idelalisib. Additional countries without an active EAP were included based on the volume of idelalisib prescribing since the time of the MA. Sites within these countries will be selected based on whether they have been prescribing idelalisib for refractory FL patients in accordance with the approved product information for idelalisib. Thus, the final number of sites per country will depend on the available number of patients per site.

This study is a non-comparative non-interventional study, as a result confounding by indication (ie confounding indicated by study drug) should be a minimal issue in the absence of a comparator. Multivariate analyses will aim to minimize potential confounding by indication by including disease assessment and according treatment in the analyses.

In reference to protocol Section 10.3 (Informed Consent) Gilead will collect informed consents for patients being identified prospectively. Informed consent will not be collected for deceased patients or patients identified retrospectively, unless specifically required by an appropriate ethics committee or required by country National Data Protection Laws for a participating centre. Not using an informed consent form (ICF) for deceased patients or patients identified in retrospect allows incorporating data which otherwise would lead to a patient population that is strongly biased towards survivors and a potential risk of death could be underestimated.

Information bias can be prevented by using standard measurement instruments, like eCRF and appropriate training of personnel entering the data. Appropriate training of personnel entering data is also important to avoid missing values when checking the patients' medical records.

Stratified analyses will be taken into consideration to account for potential behavioral changes of the site staff after the initiation of the study that might introduce bias between retrospective and prospective data collection. These stratified analyses also account for the fact that less documentation might be available in data collected retrospectively.

Patterns of missing data will be determined using the methodology outlined by Chen {Chen 1999}. Here, it has to be determined if the "Missing At Random" (MAR) criterion is fulfilled. If the assumptions of MAR or missing completely at random (MCAR) are met then a multiple imputation approach will be used. If this assumption doesn't hold, a full case or regression approach may be used.

Multiple imputation by chained equations (MICE) also referred to as sequential regression multiple imputation, is a validated statistical method for the handling of missing data {Azur 2011}. Using MICE, missing values are imputed based on the observed values for a given individual and the relationships within the data for other participants.

## **9.10. Other Aspects**

### **9.10.1. Joint Investigator/Gilead Responsibilities**

#### 9.10.1.1. Access to Information for Monitoring

The study monitor is responsible for routine review of the eCRFs at regular intervals throughout the study to verify adherence to the protocol and the completeness and consistency of the data being entered on the forms. The study monitor will only review on site the data for which patients have consented. Other data will be remotely monitored and source data will not be verified. The investigator agrees to cooperate with the study monitor to ensure that any problems detected in the course of these monitoring visits are resolved.

#### 9.10.1.2. Study Discontinuation

Gilead reserves the right to terminate the study at any time. Gilead will only terminate the study if there is sufficient cause following consultation with the PRAC. Investigator reserves the right to terminate the study at their site at any time. Should this be necessary, both parties will arrange discontinuation procedures and notify the appropriate regulatory agencies, HRECs, and IECs, in accordance with local legislation.

## **10. PROTECTION OF HUMAN SUBJECTS**

### **10.1. Good Pharmacoepidemiology and Pharmacovigilance Practices**

The study will be conducted in accordance with the guidelines of Good Pharmacoepidemiology Practices (GPPs), Heads of Medicines Agencies (HMA) Good Pharmacovigilance Practices (GVP) including archiving of essential documents.

### **10.2. Independent Ethics Committee (IEC) or Human Research Ethics Committee (HREC) Review**

Gilead (or the investigator) will submit this protocol and any accompanying material to be provided to the subject (such as advertisements, subject information sheets, or descriptions of the study used to obtain informed consent) to an IEC or HREC. The investigator will not begin patient screening/data collection until approval from the IEC or HREC has been documented and provided as a letter to the investigator.

Any subsequent modifications made to the protocol or any accompanying material to be provided to the subject after initial IEC or HREC approval will also be submitted for IEC or HREC approval prior to use, with the exception of those necessary to reduce immediate risk to study subjects.

### **10.3. Informed Consent**

Gilead will collect informed consents for patients being identified prospectively. Informed consent will not be collected for deceased patients or patients identified retrospectively, unless specifically required by an appropriate ethics committee or required by country National Data Protection Laws, for a participating centre.

All data used in this study will be anonymized and collected in an eCRF with a unique subject identifier for each patient by each participating centre. In case the IEC or HREC requires a written informed consent to be obtained the investigator will be responsible for obtaining written informed consent from each prospective patient participating in this study after adequate explanation of the aims, methods, and objectives, and alternatives of the study prior to study participation and before collection of data. The investigator must utilize the most current IEC or HREC approved consent form for documenting written informed consent. Each informed consent will be appropriately signed and dated by the subject or the subject's legally authorized representative and the person conducting the consent discussion, and also by an impartial witness if required by IEC or HREC or local requirements.

### **10.4. Confidentiality**

The investigator and Gilead must assure that subjects' anonymity will be strictly maintained and that their identities are protected from unauthorized parties. Only a unique identifier (as allowed by local law) and a unique study identification code should be recorded on any study-related document.

The investigator agrees that all information received from Gilead, including but not limited to this protocol, CRFs, and any other study information, remain the sole and exclusive property of Gilead during the conduct of the study and thereafter. This information is not to be disclosed to any third party (except employees or agents directly involved in the conduct of the study or as required by law) without prior written consent from Gilead. The investigator further agrees to take all reasonable precautions to prevent the disclosure by any employee or agent of the study site to any third party or otherwise into the public domain.

## **11. MANAGEMENT AND REPORTING OF SAFETY INFORMATION**

### **11.1. Investigator Reporting Requirements to Gilead**

The following safety information is required to be collected and reported for this study from the time the subject is prescribed idelalisib until 6 months after completion of therapy or early discontinuation of idelalisib.

- Adverse Events (AEs) leading to dose modification, interruption or discontinuation
- All Serious Adverse Events (SAEs)
- Special Situation Reports (SSRs)
- Adverse Drug Reactions (ADRs)
- Serious Adverse Drug Reactions (SADRs)
- Pregnancy or partner-pregnancy

Timelines for reporting to Gilead are as follows:

- Within 3 calendar days of knowledge of all SAEs
- Within 30 calendar days of knowledge of any non-serious AEs, SSRs, Pregnancy or partner-pregnancy

Details of the methods for reporting AEs, ADRs, SAEs, SADRs or SSRs to Gilead DSPH will be described in the CRF completion guidelines. If reporting of events is by electronic submission via eCRF, this method must always be used unless the eCRF system is not functioning. If for any reason it is not possible to record death, AE, ADRs, SAE, SADRs and SSR information electronically, the details should be recorded on the appropriate paper reporting forms (e.g., the Non-Interventional Study AE/SAE Report Form or the Non-Interventional Study Special Situations Report Form) and submitted by fax or e-mail, within the timelines given above to Gilead DSPH:

E-mail:           Safety\[contact]

[contact]

As soon as it is possible to do so, any death, AE, ADR, SAE, SADR and SSR reported via paper must be transcribed into the eCRF database according to the instructions in the eCRF completion guidelines.

### **11.1.1. Instructions for Reporting Pregnancies**

The following information is required to be collected and reported for this study if a patient or patient-partner becomes pregnant while taking idelalisib:

All pregnancies (including partner pregnancies) that occur from the time the subject is prescribed idelalisib until 6 months after completion of therapy or early discontinuation of idelalisib are to be reported to Gilead DSPH using the pregnancy report form. The pregnancy itself is not considered an AE nor is an induced elective abortion to terminate a pregnancy without medical reasons.

A non-elective premature termination of pregnancy (e.g. a spontaneous abortion, an induced therapeutic abortion due to complications or other medical reasons) must be reported within 3 calendar days as an SAE via fax or email. The underlying medical reason for this procedure should be recorded as the SAE term. A spontaneous abortion is always considered to be an SAE. Furthermore, any SAE occurring as an adverse pregnancy outcome post study must be reported to Gilead DSPH.

Timelines for reporting to Gilead are as follows:

- Within 30 calendar days of knowledge of the pregnancy
- Within 3 calendar days of knowledge of all pregnancy related serious adverse events (regardless of causality, e.g., a spontaneous abortion, hospitalization, etc.)

Pregnancy information should be reported on the pregnancy report form, and the outcome should be reported on pregnancy outcome report form. However, if the event qualifies as an SAE then an SAE form should be completed. If reporting of events is by electronic submission via eCRF, this method must always be used unless the eCRF system is not functioning. If for any reason it is not possible to record pregnancy or pregnancy outcome information electronically, the details should be recorded on the appropriate paper reporting form and submitted by fax or e-mail, within the timelines given above to Gilead DSPH:

E-mail: Safety\[contact]

[contact]

As soon as it is possible to do so, any pregnancy or pregnancy outcome reported via paper must be transcribed into the eCRF database according to the instructions in the eCRF completion guidelines.

### **11.2. Gilead Reporting Requirements to Regulatory Authorities**

Gilead is responsible for analysing reports of all safety information and reporting to regulatory agencies as determined by country-specific legislation or regulations.

Assessment of expectedness for all safety reports will be determined by Gilead using reference safety information specified in the product label.

### 11.3. Definitions

#### 11.3.1. Adverse Events

An **adverse event** (AE) is any untoward medical occurrence in a clinical study subject administered a pharmaceutical product, which does not necessarily have a causal relationship with the treatment. An AE can therefore be any unfavourable and/or unintended sign, symptom, or disease temporally associated with the use of a medicinal product, whether or not considered related to the medicinal product. AEs may also include lack of efficacy, overdose, drug abuse/misuse reports, or occupational exposure. Pre-existing events that increase in severity or change in nature during or as a consequence of participation in the clinical study will also be considered AEs.

This study will only collect AEs that lead to dose modification, interruption or discontinuation.

An AE does not include the following:

- Medical or surgical procedures such as surgery, endoscopy, tooth extraction, and transfusion. The condition that led to the procedure may be an AE and should be reported.
- Situations where an untoward medical occurrence has not occurred (e.g., hospitalization for elective surgery, social and/or convenience admissions)
- Any medical condition or clinically significant laboratory abnormality with an onset date before the consent form is signed. These are considered to be pre-existing conditions and should be documented on the medical history CRF (if applicable).

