##### Treatment history:

- Prior treatment regimens for FL:
  - Drug names for each regimen
  - Number of cycles or duration that regimen administered
  - Reasons for discontinuation

Idelalisib treatment (start date, dose at baseline)

Co-medications:

- Current medications
- Name of medication
- Indication
- Start date or estimated duration on medication

Routine laboratory parameters and results (when available):

- Hemoglobin, erythrocyte count; total leukocytes, absolute neutrophil count, lymphocytes, monocytes, platelet count
- Serum chemistry including sodium, potassium, urea, uric acid, creatinine, lactate dehydrogenase (LDH)
- Liver function test: ALT, AST, ALP, GGT, total bilirubin, albumin, total protein

*During observation period (visits based on local clinical practice, collected retrospectively and prospectively):*

Collection of SAEs, SSRs, ADRs and SADR (see protocol section 11.1). Focus will be given to HOIs:

- any grade bowel perforation
- grade 3 diarrhoea and/or colitis
- any grade PML
- any grade pneumonitis
- grade 3 rash by MST
- infection (specifically grade 3 infection, grade 3 febrile neutropenia, grade 3 neutropenia, any grade CMV infection, and any grade PJP)
- Transaminase elevation
- SJS-TEN

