### **9.4. Data Sources**

The primary data source will be the patient's medical records. Review of electronic or paper medical records, data identification, abstraction and data transcription will be performed by trained site personnel. This will include all safety information that is entered into the patient's medical records (i.e., events and special situations). Data capture is electronic and therefore data collection will occur at time of data entry by the site. The investigator will seek to ensure data entry for retrospective data is conducted as close as possible to the identification of an eligible subject at the start of the study and prospective data as close as possible at the time of each patient's visit.

All data will be anonymised and collected for those patients meeting all eligibility criteria. Each patient will be identified by a unique eCRF generated subject identifier. For the retrospective data, medical record abstraction will be performed by internal study team members of the site, who will be trained on the abstraction method to ensure records are acceptable for review and inclusion in the study.

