#### **11.4. Clinical Laboratory Abnormalities**

Laboratory abnormalities without clinical significance are not recorded as safety events. However, laboratory abnormalities (e.g., clinical chemistry, hematology, and urinalysis) that require medical or surgical intervention or lead to drug interruption, modification, or discontinuation and considered to be causally associated with the medicinal product must be recorded as an AE, or an SAE, if applicable. In addition, laboratory or other abnormal assessments (e.g., electrocardiogram, x-rays, vital signs) that are associated with signs and/or symptoms must be recorded as an AE or SAE if they meet the definition of an AE or SAE as described in Section 11.3. If the laboratory abnormality is part of a syndrome, record the syndrome or diagnosis (e.g., anemia), not the laboratory result (i.e., decreased hemoglobin).

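### The protocol's sections disagree on which events are abstracted, so listed health outcomes of interest that are non-serious, judged unrelated and not dose-changing may be missed

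*Protocol*

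**What the plan says.** Five sections of the protocol bear on which events reach the database.

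- **Section 9.3 (repeated in the synopsis).** The instruction for the observation period is "Collection of SAEs, SSRs, ADRs and SADR (see protocol section 11.1). Focus will be given to HOIs". The list that follows has bowel perforation, PML and pneumonitis at any grade. Diarrhoea/colitis, rash, infection and febrile neutropenia are listed at grade 3. The infection item ends with "grade 3 neutropenia, any grade CMV infection, and any grade PJP". Transaminase elevation and SJS-TEN carry no grade. The same section collects neutrophil counts, ALT and AST during observation, when available.
- **Section 11.1.** The reportable set is "Adverse Events (AEs) leading to dose modification, interruption or discontinuation", all SAEs, special situation reports, ADRs, serious ADRs and pregnancies. HOIs are not a category of their own.
- **Section 11.3.1.** "This study will only collect AEs that lead to dose modification, interruption or discontinuation".
- **Section 11.4.** The rule covers laboratory abnormalities that call for treatment, and likewise those that "lead to drug interruption, modification, or discontinuation and considered to be causally associated with the medicinal product must be recorded as an AE"; the causal condition applies to both groups. The other route is an abnormality with signs or symptoms that meets the AE or SAE definition.
- **Section 9.4.** On record abstraction: "This will include all safety information that is entered into the patient's medical records (i.e., events and special situations".

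Section 8 promises rates for SAEs and names the HOIs as the focus.

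**The concern.** An outcome defined at any grade implies that all occurrences are counted. The reporting rule instead filters them by seriousness, the investigator's causality opinion and whether dosing changed. Anything failing all three tests has no route into the event data under Section 11, while Section 9.4 tells the same abstractor to take everything in the record. Two sites could both follow the protocol and capture different events.

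This matters because the study is single-arm and its output is occurrence. The checklist in Annex 1 says that only crude and adjusted incidence rates will be calculated and that no comparisons will be made, so there is no control group in which under-capture could cancel. Section 9.7 also plans time-to-event models for AESIs, listed separately from ADRs and serious ADRs, yet Section 11 has no collection route for them as such.

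**Working it through.** **Step 1. Apply each rule to example events.** The last column assumes that the event is noted in the record.

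| Event | Listed in 9.3 | Reportable under 11.1 with 11.3.1 | Required by 11.4 | Abstracted under 9.4 |
|---|---|---|---|---|
| Mild pneumonitis or CMV infection: non-serious, judged unrelated, no dose change | Yes | No | Not applicable | Yes |
| Grade 3 rash or infection managed without admission: not medically important, judged unrelated, no dose change | Yes | No | Not applicable | Yes |
| Asymptomatic transaminase rise: dose interrupted, judged unrelated, non-serious | Yes | Yes (dose-changing) | No (not judged causal) | Yes |
| Asymptomatic grade 3 neutropenia: no intervention, no dose change, judged unrelated | Yes | No, unless classed as medically important | No | Yes; also in the laboratory data if measured |
| Bowel perforation, PML, PJP | Yes | In most cases, as serious | Not applicable | Yes |

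Rows 1 and 2 show the gap. Row 3 shows that 11.4 is narrower than 11.1 for the same event. Row 4 shows that the laboratory HOIs have a second source.

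The sentence in 11.3.1 cannot be read alone: taken literally it would exclude SAEs that change no dose, which 11.1 requires. The three-way test comes from 9.3, 11.1 and 11.3.1 together.

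**Step 2. Reproduce the plan's precision (Section 9.5).** With n = 1.96² p(1 − p)/d²:

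- p = 3.2%, d = 0.02: n = 298
- p = 5.2%, d = 0.025: n = 303
- p = 7.6%, d = 0.03: n = 300

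The stated 300 is reproduced as the size for a two-sided 95% interval on a single proportion. The plan counts patient-years; I use 300 as the plan does, as n.

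**Step 3. Compare possible bias with that precision.** If a share u of true HOIs is not captured, the observed proportion is p(1 − u) and the bias is −pu. The bias equals the half-width h = 1.96 √(p(1 − p)/300) when u = h/p. Using the proportions quoted in Section 9.5:

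| Outcome | p | h (points) | u at which bias = h |
|---|---|---|---|
| Grade 3 diarrhoea/colitis | 1.4% | 1.33 | 95% |
| Grade 3 febrile neutropenia | 2.0% | 1.58 | 79% |
| Grade 3 infection | 6.1% | 2.71 | 44% |
| Grade 3 rash | 8.1% | 3.09 | 38% |

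The protocol gives no proportion for pneumonitis or CMV infection, so these four serve only as a scale.

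**Step 4. Illustrate u.** The documents give no value. Assume that 30–70% of HOIs are non-serious, 20–50% judged unrelated and 30–50% without dose change, independently. Then u runs from 0.3 × 0.2 × 0.3 = 1.8% to 0.7 × 0.5 × 0.5 = 17.5%. At p = 6.1% the bias is 0.018 × 6.1 = 0.11 to 0.175 × 6.1 = 1.07 points, against h = 2.71. If mild events also tend to be judged unrelated and to change no dose, independence understates u. The range is an illustration, not an estimate.

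**The case against.** The strongest reply is that the filter is wide. Seriousness in Section 11.3.2 includes medically important events and gives blood dyscrasias without hospitalization as an example. Under Section 11.5 a reasonable possibility is enough for relatedness, while a negative answer needs evidence of another cause. An event must fail all three tests to be lost. This stands: it narrows the gap to the milder or outpatient events in Step 1, but does not close it.

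Second, a reader might infer that neutropenia and transaminase elevation suffer most because Section 11.4 is strict. The documents do not support that. Section 11.4 governs when an abnormality becomes a safety event; it does not restrict the laboratory values collected under Section 9.3. Both HOIs can be derived from those values, and an analysis plan may say so. The remaining risk is counting from event reports, or values that are missing.

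Third, a reader might infer that the study is committed to an all-cause, all-grade incidence for every HOI. Section 8 promises rates explicitly only for SAEs, and the Poisson models in Section 9.7 are for ADRs and serious ADRs. The wider commitment is a reading of Sections 8 and 9.3 together, though an any-grade definition serves little purpose if milder events need not be recorded.

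Fourth, sites may follow Section 9.4, or completion guidelines that are not shown, and capture everything. That is possible, but the protocol should not leave it to chance.

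**Conclusion.** The inconsistency is established from the text: Sections 9.3, 9.4, 11.1, 11.3.1 and 11.4 do not define one set of events to abstract. Under-ascertainment is possible for the clinical HOIs and conditional for the laboratory ones. The direction is firm, since this filter can only remove events; the size is not, because the uncaptured share is not in the documents. A reader might conclude that the HOI rates will be too low by a material amount. That goes too far: sites following Section 9.4 would lose nothing by this route, and under the assumed shares in Step 4 the bias stays inside the planned half-width.

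Nor do the documents show that the filter acts differently on chart-abstracted and contemporaneous events. Section 9.3 says that the variables are identical, and Section 9.7 plans stratified analyses. Stratifying could reveal such a difference but could not restore events that were not collected.

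The point still deserves correction, because this bias does not shrink with more patients and no analysis plan can repair it for the clinical HOIs.

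**What to change.** 1. Add to Sections 11.1 and 11.3.1 that every HOI listed in Section 9.3 is recorded regardless of seriousness, causality or action taken.
2. Exempt the listed HOIs from the conditions in Section 11.4.
3. State that the neutropenia and transaminase HOIs are graded from the neutrophil, ALT and AST values already collected, supplemented by event reports where values are unavailable. Give transaminase elevation a grade, or state that it is any grade.
4. Reword Section 9.4 so that it describes the same set of events as Section 11.3.1.

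The cost is protocol wording, one eCRF line and slightly more abstraction for non-serious HOIs; the laboratory values are already collected. It is cheapest before the first patient is entered, since a later change means returning to records already abstracted.

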## **9. RESEARCH METHODS**

### **9.1. Study Design**

A retrospective cohort study enrolling patients who were or are being treated with idelalisib for refractory FL according to the product information and treatment guidelines in routine clinical practice after the country specific approval date.

Patient's data will be collected from the date of treatment initiation with idelalisib until 6 months after treatment discontinuation.

The study design allows for both retrospective and prospective data to be collected. The start of data collection is defined as the entry of the first patient into the eCRF. In the data analysis, any data prior to the start of the study will be considered retrospective. Any data after that date will be considered prospective.

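### The adverse event definition cuts off at signed consent, which contradicts a safety window that opens at idelalisib prescription and cannot be applied to patients who sign no form

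*Protocol*

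**What the plan says.** Section 11.3.1 lists what is not an AE. The last item is any medical condition or "clinically significant laboratory abnormality with an onset date before the consent form is signed. These are considered to be pre-existing conditions", to be recorded on the medical history form where applicable. The same section keeps one kind of earlier event: "Pre-existing events that increase in severity or change in nature during or as a consequence of participation in the clinical study" still count as AEs.

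Two other sections set the observation period without reference to consent. Section 11.1 requires safety information "from the time the subject is prescribed idelalisib until 6 months after completion of therapy or early discontinuation of idelalisib". Section 9.1 says: "Patient's data will be collected from the date of treatment initiation with idelalisib until 6 months after treatment discontinuation".

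Section 10.3 says who signs: "Informed consent will not be collected for deceased patients or patients identified retrospectively, unless specifically required by an appropriate ethics committee", or by national data protection law. Section 9.9 gives the reason. Without this waiver, the study "would lead to a patient population that is strongly biased towards survivors and a potential risk of death could be underestimated".

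**The concern.** A consent-date cut-off suits a trial in which consent precedes the first dose. This cohort is observed from the start of a marketed treatment that may have begun long before the study reached the site. Some patients will have no signature. For others, the signature may come after exposure began.

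The primary objective is to describe the safety profile of idelalisib through event rates. If person-time runs from treatment initiation but events count only from signature, numerator and denominator no longer match, and the error goes one way, towards fewer events. Early toxicity would be most exposed.

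A reclassified event may also have nowhere to go. Section 9.6 builds the eCRF from the variables in Section 9.3, whose medical history block lists only lymphoma history and ECOG status. Monitoring would not reliably catch the loss. Under Section 9.10.1.1, source data of patients without consent are not verified. For patients with consent, the monitor checks adherence to a protocol that contains this clause.

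**Working it through.** The clause rests on no figure, so the main check sets the rules side by side.

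**1. The rules applied to each kind of patient**

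- *Signs before idelalisib is prescribed.* Every event in the Section 11.1 window follows signature. There is no conflict.
- *Signs after starting idelalisib.* Examples are a retrospective patient in a centre or country that requires consent, or a prospective patient who signs after the first dose. For a new event between first dose and signature, 11.1 says report it and 11.3.1 says it is medical history. The worsening provision does not help, because the event did not exist before treatment.
- *Never signs.* Section 11.3.1 supplies no date. A site may conclude that the clause never applies, or that no event can be shown to follow consent. The protocol does not choose.

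**2. Which event classes are exposed**

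- The clause stands only in the AE definition. Its direct target is the AEs that this study collects: those leading to dose modification, interruption or discontinuation.
- SAEs (11.3.2) and adverse drug reactions, ADRs (11.3.4), have their own definitions, which do not repeat it. An SAE is still an adverse event by name, a serious ADR is defined as a related SAE (11.3.5), and 11.4 refers abnormal findings back to the Section 11.3 definitions. For SAEs and HOIs, exposure is therefore possible but not established.

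**3. Direction**

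Let E be the true number of events and T the person-time from treatment initiation. If a fraction f of events is moved to medical history and T is kept:

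observed rate = (1 − f) × E / T, so the relative bias is −f.

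Here f = w × s, where w is the share of all events that belong to patients who sign late, and s is the share of those patients' events with onset before signature. The protocol gives neither w nor s. Among late signers the relative bias is −s; among patients who sign before prescription it is 0. The loss therefore differs by consent status. It could also distort the comparison of retrospective with prospective data that Section 9.7 plans as protection against bias.

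**4. Scale, for illustration only**

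Section 9.5 plans 300 to estimate 3.2% with precision 0.02. With a 95% interval (the level in Section 9.7):

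n = 1.96² × 0.032 × 0.968 / 0.02² = 297.5, which reproduces the plan's 300. The formula counts persons, whereas Section 9.5 says patient-years; that is a separate matter.

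Take the 6.1% for grade 3 infection in Section 9.5, with n = 300:

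- Expected events: 300 × 0.061 = 18.3.
- 95% half-width: 1.96 × √(0.061 × 0.939 / 300) = 0.027, or 2.7 percentage points.
- Assumed f = 10%: 16.5 events remain, 5.5%, a fall of 0.6 points.
- Assumed f = 25% (for instance w = 0.5 and s = 0.5): 13.7 events remain, 4.6%, a fall of 1.5 points.
- The bias reaches the half-width at f = 0.0271 / 0.061 = 44%.

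These values of f are assumptions chosen to show scale. They do not estimate what would happen.

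**The case against.** The strongest reply is that the intent is plain elsewhere. Section 11.1 is the operative reporting instruction and opens at prescription. Section 9.3 collects SAEs and ADRs both retrospectively and prospectively. Section 9.4 says abstraction covers all safety information in the medical record. Section 6 schedules an interim report on retrospective data, which would make little sense if events before consent were discarded. This stands as far as it goes: loss is possible, not certain. It does not remove the conflict, because no section ranks the rules, and a site that follows 11.3.1 to the letter would be following the protocol.

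The exposed group may also be small. Section 9.7 describes prospective patients as those prescribed idelalisib after study start, and Section 10.3 places any required written consent before data collection. Patients found by record search give no consent by default. This also stands: direct loss is confined to patients who sign after starting treatment, and the protocol does not say how many there are.

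A reader might infer that the clause wipes out on-drug events in most of the cohort, on the ground that most patients never sign. The documents do not support that. They give no count of patients without consent. The windows of about 3 and 2.5 years suggest a retrospective share of 3 / 5.5 = 55%, but only if accrual is uniform. More importantly, a patient with no signature faces an undefined cut-off, which is not the same as automatic exclusion.

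**Conclusion.** The contradiction is real and concerns a stated rule, not detail that could be left to an analysis plan. Section 11.3.1 conflicts with Sections 9.1 and 11.1 and cannot be applied to patients who, under Sections 9.9 and 10.3, sign no form. Applied literally to patients who sign after starting idelalisib, it would drop new on-drug events and keep the person-time. AE rates would be biased downwards, and differently by consent status. SAE and HOI rates may be affected, depending on how sites read the definitions.

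No study-level size follows from the documents. The illustration rests on assumed fractions of reclassified events and on treating 300 as persons. A reader might go further and claim that every SAE, ADR and HOI rate is biased, or attach a percentage based on a consent lag. The first is not shown, because the SAE and ADR definitions do not carry the clause. The second has no source, because no lag is given.

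Selection of survivors in centres that require consent is a separate question, which Section 9.9 already recognises. It is not part of this point.

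**What to change.** - In Section 11.3.1, replace the consent date with the start of the Section 11.1 safety window, for all patients whatever their consent status.
- Choose one anchor, either prescription or treatment initiation, and use it in Sections 9.1, 11.1 and 11.3.1. At present 11.1 uses the former and 9.1 the latter.
- State that a new event with onset after that anchor is never medical history.
- Align the eCRF completion guidelines before sites begin abstraction.

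The cost is a few sentences in the protocol and the matching text in the guidelines. The planned size and precision do not change, and no patients or procedures are added.
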